### 6.3. Sample Storage

CCI

CCI

#### 6.4. Blood Collection

The maximum amount of blood to be drawn at a visit is ~114 mL and the total amount of blood to be drawn over the initial 52-week study period (including the 4-week screening period, through Week 48 of the study, and with a possible end-of-study visit) is ~587 mL. For a 40-kg person (the smallest participant expected to enroll in the study), this equates to maximum blood volume per body weight per visit of ~2.9 mL/kg and a total blood volume per body weight per average 6-week period of ~1.7 mL/kg. These quantities of blood are within accepted limits of 3.0 mL/kg of body weight for a single blood draw and 7.0 mL/kg of body weight for a 6-week period.

Specific details regarding blood sample collection and processing requirements will be provided separately in the laboratory manual.

CCI

#### 6.5. Study Procedure Rationale

The planned study assessments and timing have been selected as appropriate for screening of subjects, for determination of drug- or disease-related toxicities, for dose modification during the study, for characterization of drug exposure and desired pharmacological effects, and for evaluation of drug activity. The scheduling of testing is designed to collect a complete safety and pharmacology data set while maintaining subject tolerance of study procedures. The planned schedule of tumor assessments is consistent with expected rate of changes and appropriately balances precise measurement of tumor control with the expense and subject inconvenience associated with clinical and radiological procedures. For discussion of the rationale for endpoint selection, see Section 3.5.

## 7. EFFICACY ASSESSMENTS

### 7.1. Tumor Status Assessments

The determination of CLL response and progression will be based on standardized IWCLL criteria {[Hallek 2008](#)}, as specifically modified for this study to reflect current recommendations which consider the mechanism of action of idelalisib and similar drugs {[Cheson 2012](#)}. During the course of the study, investigators will assess the status of each subject's CLL according to schedule. If CLL progression is suspected, the IRC will be notified and will review radiographic and pertinent clinical data in order to provide expert interpretation (see Section [10.4.2](#)). The findings of the IRC will be considered primary for analyses of PFS and other tumor control endpoints.

### 7.2. Method of Assessment

Imaging-based evaluation will be used in this study in all subjects enrolled. CT scan is the preferred method for radiographic tumor assessment. MRI scanning may be used at the investigator's discretion in subjects for whom this may be a preferred alternative to CT scanning; however, if MRI is performed, a non-contrast CT of the chest should be performed. Contrast-enhanced scanning is preferred, but iodine-containing or gadolinium contrast material may be omitted in subjects for whom use of a contrast agent would be medically contraindicated. Chest x-ray, ultrasound, endoscopy, laparoscopy, PET, radionuclide scans, or tumor markers will not be considered for response assessment.

For radiographic evaluations, the same method of assessment and the same technique (eg, scan type, scanner, subject position, dose of contrast, injection/scan interval) should be used to characterize each identified and reported lesion at baseline and during study treatment and follow-up. All relevant clinical and radiographic information required to make each tumor status assessment must be made available for source verification and for submission to the IRC (see Section [10.4.2](#)).

### 7.3. Timing of Assessments

During screening, clinical and imaging-based tumor assessments should be performed within the specified screening period. Clinical tumor assessments should be performed at each designated clinical visit (see [Appendix 7](#)). On-study CT/MRI tumor assessments should be performed as indicated in [Appendix 7](#), until ~129 events have been observed in the study population. An end-of-study CT/MRI tumor assessment should be performed unless the subject already has radiographic confirmation of disease progression  $\leq 4$  weeks prior. If a subject permanently discontinues study drug prior to objective documentation of CLL progression, investigators should continue further follow-up according to the protocol specified schedule until CLL progression is documented by the central IRC.

## **7.4. Identification and Measurement of Tumor Lesions and Organomegaly**

### **7.4.1. Index Lesions**

At baseline, up to 6 lymph nodes should be selected as index lesions that will be used to quantitate the status of the disease during study treatment. Ideally, the index lesions should be located in disparate regions of the body. Only peripheral nodes need be selected as index lesions. However, it is optimal if mediastinal and retroperitoneal areas of disease are assessed whenever these sites are involved.

Index lesions will be measured and recorded at baseline and at the stipulated intervals during treatment. The cross-sectional dimensions (the largest cross-sectional diameter, ie, the LD × the LPD will be recorded (in cm) for each index lesion. The product of the perpendicular diameters (PPD) for each index lesion and the SPD for all index lesions will be calculated and recorded. The baseline SPD will be used as references by which objective tumor response will be characterized during treatment. The nadir LD of individual lesions and the nadir SPD will be used as references by which CLL progression will be characterized. All LD and LPD diameters will be reported in centimeters and all PPDs and SPDs will be reported in centimeters squared.

A nodal mass may be selected as a nodal index lesion if it is both abnormal and measurable at baseline. A lymph node lesion is considered abnormal if it has a single diameter that is > 1.5 cm and is considered measurable if it has 2 perpendicular diameters that can be accurately measured in cross section with the LD being ≥ 1.0 cm and the LPD also being ≥ 1.0 cm.

Index lesions measuring > 1.5 cm in the LD and > 1.0 cm in the LPD, will be prioritized during baseline index lesion selection.

At follow-up time points, the LDs for individual lesions and the SPD of all nodal index lesions will be considered. Because nodal index lesions that have one or both diameters > 0 cm and < 1.0 cm cannot be reliably measured, a default value of 1.0 cm will be assigned for each diameter that meets these criteria and the resulting PPD will be used in SPD calculations. Based on this convention, a CR may be achieved even if an SPD value is > 0 cm^2, (ie, if all lymph nodes measure < 1.0 cm^2).

A new node that measures > 1.5 cm in the LD and > 1.0 cm in the LPD will be considered progressive disease.

In cases in which a large lymph node mass has split into multiple components, all subcomponents regardless of size will be used in calculating the SPD. Progression of the lesion will be based on the SPD of sub-components. Lesion sub-components will have the true PPDs calculated. Similarly, lesion sub-components that are visible but neither abnormal nor measurable will have the default PPD of 1.0 cm^2 (1.0 cm × 1.0 cm) used in calculating the SPD.

If lesions merge, a boundary between the lesions will be established so the LD of each individual lesion can continue to be measured. If the lesions have merged in a way that they can no longer be separated by this boundary, the newly merged lesion will be measured bi-dimensionally.

### 7.4.2. Spleen and Liver

Both the spleen and liver should be assessed by physical examination and by CT/MRI scan at baseline and at the stipulated intervals during treatment. The baseline and nadir values for the longest vertical dimension (LVD) of each organ will be used as reference to further characterize the objective tumor response of the measurable dimensions of the CLL during treatment. All spleen and liver LVD measurements should be recorded in centimeters.

By imaging, the spleen will be considered enlarged if it is >12 cm in LVD {Bezerra 2005}, {Asgar 2011}, with the LVD being obtained by multiplying the number of sections on which the spleen is visualized by the thickness of the sections (eg, if the spleen is seen in 14 contiguous cross-sectional images with 0.5-cm thickness, the LVD is recorded as 7 cm).

For subjects with splenomegaly at baseline or at the splenic LVD nadir, respective response and progression evaluations of the spleen will consider only changes relative to the enlargement of the spleen at baseline or nadir, not changes relative to the total splenic LVD.

A 50% decrease (minimum 2 cm) from baseline in the enlargement of the spleen in its LVD or decrease to  $\leq 12$  cm in the s LVD is required for declaration of a splenomegaly response. Conversely, an increase in splenic enlargement by  $\geq 50\%$  (minimum increase of 2 cm) from nadir is required for declaration of splenic progression.

By imaging, the liver will be considered enlarged if it is > 18 cm in LVD {Erturk 2006}.

A 50% decrease (minimum 2 cm) from baseline in the enlargement of the liver in its LVD or to  $\leq 18$  cm in the LVD is required for declaration of a hepatomegaly response. Conversely, an increase in liver enlargement by  $\geq 50\%$  (minimum increase of 2 cm) from nadir is required for declaration of hepatic progression.

### 7.4.3. Non-Index Lesions

Any other measurable and abnormal nodal lesions not selected for quantitation as index lesions may be considered non-index lesions. In addition, non-measurable evidence of CLL such as nodal lesions with both diameters < 1.0 cm, extra-nodal lesions, bone lesions, leptomeningeal disease, ascites, pleural or pericardial effusions, lymphangitis of the skin or lung, abdominal masses that are not confirmed and followed by imaging techniques, cystic lesions, previously irradiated lesions, lesions with artifacts may be considered as non-index disease.

The presence or absence of non-index disease should be recorded at baseline and at the stipulated intervals during treatment. If present at baseline, up to 6 non-index lesions should be recorded. The non-index disease at baseline will be used as a general reference to further characterize regression or progression of CLL during assessments of the objective tumor response during treatment. Measurements are not required and these lesions should be followed as “present” or “absent”.

## 7.5. Definitions of Tumor Response and Progression

Responses will be categorized by the IRC as CR, PR, SD, or PD. In addition, a response category of not evaluable (NE) is provided for situations in which there is inadequate information to otherwise categorize response status. A response category of no disease (ND) is included for situations in which there is absence of tumor both at baseline and on treatment.

The best overall response will be determined. The best overall response is the best response recorded from the start of treatment until progressive disease/recurrence (taking as reference for PD the smallest measurements recorded since treatment started). BOR of CR or PR needs to be maintained at least 8 weeks to confirm a response. Subjects who initially responded but did not have an evaluable follow-up visit or did not maintain a response (i.e. progressed) for at least 8 weeks will not be counted as a confirmed responder. Subjects with a best overall response of NE or ND will be counted in the denominators in calculations of tumor response rates. Where imaging data are available, these data will supersede physical examination data in determining tumor status.

### 7.5.1. Complete Response

To satisfy criteria for a CR, all of the following criteria must be met:

- No evidence of new disease
- ALC in peripheral blood of  $< 4 \times 10^9/L$
- Regression of all index lesions to normal size  $\leq 1.5$  cm in the LD
- Normal spleen and liver size
- Regression to normal of all nodal non-index disease and disappearance of all detectable non-nodal, non-index disease
- Morphologically negative bone marrow defined as  $< 30\%$  of nucleated cells being lymphoid cells and no lymphoid nodules in a bone marrow sample that is normocellular for age
- Peripheral blood counts meeting all of the following criteria:
  - ANC  $> 1.5 \times 10^9/L$  without need for exogenous growth factors (eg, G-CSF)
  - Platelet count  $\geq 100 \times 10^9/L$  without need for exogenous growth factors
  - Hemoglobin  $\geq 110$  g/L (11.0 g/dL) without red blood cell transfusions or need for exogenous growth factors (eg, erythropoietin)

***Note: Subjects who fulfill all the criteria for a CR (including bone marrow criteria) but who have a persistent anemia, thrombocytopenia, or neutropenia or a hypocellular bone marrow that is related to prior or ongoing drug toxicity (and not to CLL) will be considered as a CR with incomplete marrow recovery (CRi).***

### 7.5.2. Partial Response

To satisfy criteria for a PR, all of the following criteria must be met:

- No evidence of new disease
- A change in disease status meeting  $\geq 2$  of the following criteria, with 2 exceptions in which only 1 criterion is needed: (1) Only lymphadenopathy is present at baseline; (2) Only lymphadenopathy and lymphocytosis are present at baseline. In these 2 cases, only lymphadenopathy must improve to the extent specified below:
  - In a subject with baseline lymphocytosis ( $ALC \geq 4 \times 10^9/L$ ), a decrease in peripheral blood ALC by  $\geq 50\%$  from baseline or a decrease to  $< 4 \times 10^9/L$
  - A decrease by  $\geq 50\%$  from the baseline in the SPD of the index nodal lesions
  - In a subject with enlargement of the spleen at baseline, a splenomegaly response as defined in Section 7.4.2
  - In a subject with enlargement of the liver at baseline, a hepatomegaly response as defined in Section 7.4.2
  - A decrease by  $\geq 50\%$  from baseline in the CLL marrow infiltrate or in B-lymphoid nodules
  - No index, splenic, liver, or non-index disease with worsening that meets the criteria for definitive PD
- Peripheral blood counts meeting  $\geq 1$  of the following criteria:
  - $ANC \geq 1.5 \times 10^9/L$  or  $\geq 50\%$  increase over baseline without need for exogenous growth factors (eg, G-CSF)
  - Platelet count  $\geq 100 \times 10^9/L$  or  $\geq 50\%$  increase over baseline without need for exogenous growth factors
  - Hemoglobin  $\geq 110$  g/L (11.0 g/dL) or  $\geq 50\%$  increase over baseline without red blood cell transfusions or need for exogenous growth factors (eg, erythropoietin)

### 7.5.3. Stable Disease

To satisfy criteria for SD, the following criteria must be met:

- No evidence of new disease
- There is neither sufficient evidence of tumor shrinkage to qualify for PR nor sufficient evidence of tumor growth to qualify for definitive PD

#### 7.5.4. Definitive Progressive Disease

The occurrence of any of the following events indicates definitive PD:

- Evidence of any new disease:
  - A new node that measures > 1.5 cm in the LD and >1.0 cm in the LPD
  - New or recurrent splenomegaly, with a minimum LVD of 14 cm
  - New or recurrent hepatomegaly, with a minimum LVD of 20 cm
  - Unequivocal reappearance of an extra-nodal lesion that had resolved
  - A new unequivocal extra-nodal lesion of any size
  - New non-index disease (eg, effusions, ascites, or other organ abnormalities related to CLL)

***Note: Isolated new effusions, ascites, or other organ abnormalities are not sufficient evidence alone of PD unless histologically confirmed. Thus, a declaration of PD should not be made if this is the only manifestation of apparently new disease.***

- Evidence of worsening of index lesions, spleen or liver, or non-index disease:
  - Increase from the nadir by  $\geq 50\%$  in the SPD of index lesions
  - Increase from the nadir by  $\geq 50\%$  in the LD of an individual node or extra-nodal mass that now has an LD of >1.5 cm and an LPD of > 1.0 cm
  - Splenic progression, defined as an increase in splenic enlargement by  $\geq 50\%$  from nadir (with a minimum 2 cm increase and a minimum LVD of 14 cm)
  - Hepatic progression, defined as an increase in splenic enlargement by  $\geq 50\%$  from nadir (with a minimum 2 cm increase and minimum LVD of 20 cm)
  - Unequivocal increase in the size of non-index disease (eg, effusions, ascites, or other organ abnormalities related to CLL)
  - Transformation to a more aggressive histology (eg, Richter syndrome) as established by lymph node or other tissue biopsy, or fluid cytology (with the biopsy or fluid cytology date being considered the date of CLL progression if the subject has no earlier objective documentation of CLL progression).

- Decrease in platelet count or hemoglobin that is attributable to CLL, is not attributable to an autoimmune phenomenon, and is confirmed by bone marrow biopsy showing an infiltrate of clonal CLL cells
  - The current platelet count is  $< 100 \times 10^9/L$  and there has been a decrease by  $> 50\%$  from the highest on-study platelet count
  - The current hemoglobin is  $< 110 \text{ g/L}$  ( $11.0 \text{ g/dL}$ ) and there has been a decrease by  $> 20 \text{ g/L}$  ( $2 \text{ g/dL}$ ) from the highest on-study hemoglobin

***Note: If there is uncertainty regarding whether there is true progression, the subject should continue study treatment and remain under close observation (eg, evaluated at 4-week intervals) pending confirmation of progression status by the IRC. In particular, worsening of constitutional symptoms in the absence of objective evidence of worsening CLL will not be considered definitive disease progression; in such subjects, both CLL-related and non-CLL-related causes for the constitutional symptoms should be considered. Worsening of disease during temporary interruption of study treatment (eg, for intercurrent illness) is not necessarily indicative of resistance to study treatment. In these instances, CT/MRI or other relevant evaluations should be considered in order to document whether definitive disease progression has occurred. If subsequent evaluations suggest that the subject has experienced persistent definitive CLL progression, then the date of progression should be the timepoint at which progression was first objectively documented.***

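### The SPD progression trigger has no size floor, so with the 1.0 cm default and the split-node rule it can score definitive PD when every index node is normal-sized

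*Protocol*

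**What the plan says.** Section 7.5.4 opens its list with "The occurrence of any of the following events indicates definitive PD", so each item suffices alone. One item is an increase from nadir of at least 50% "in the SPD of index lesions". It carries no further condition.

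The neighbouring triggers do:
- An individual node with a 50% rise in LD counts only if it is one "that now has an LD of >1.5 cm and an LPD of > 1.0 cm".
- New nodal disease requires "A new node that measures > 1.5 cm in the LD and >1.0 cm in the LPD".
- Splenic progression is qualified "with a minimum 2 cm increase and a minimum LVD of 14 cm". Hepatic progression has a 2 cm increase and a 20 cm minimum.

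Section 7.4.1 sets the measuring conventions. For an index node with a diameter above 0 but below 1.0 cm, "a default value of 1.0 cm will be assigned for each diameter that meets these criteria"; a node that has disappeared gets no default. When a mass splits, "all subcomponents regardless of size will be used in calculating the SPD", progression of the lesion is judged on that sum, and fragments that are visible but neither abnormal nor measurable are entered at 1.0 cm² each.

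The same section treats a node as abnormal only if a diameter exceeds 1.5 cm. The nodal part of CR in Section 7.5.1 is "Regression of all index lesions to normal size", meaning an LD of 1.5 cm or less.

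**The concern.** A ratio to nadir becomes unstable when the nadir is small. The protocol guards against this in every comparable trigger except SPD. The default adds a second problem: moving from invisible to barely visible adds a full 1.0 cm² per node, and a remnant that breaks into small pieces can gain SPD while it shrinks. One scan can then satisfy both the nodal size criterion for CR and the definition of definitive PD.

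The rule is also inconsistent with its neighbours. A wholly new 1.4 cm node is not progression, but a 0.3 cm trace of an old index node can be.

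Definitive PD is the primary endpoint event (Section 3.3) and, once confirmed by the IRC, a reason to stop study drug and possibly to end participation (Sections 5.8 and 5.9). A false call therefore enters the primary analysis directly, and the later scans that would expose it may be lost.

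**Working it through.** **Inputs (Sections 7.4.1, 7.5.1, 7.5.4).** PPD = LD x LPD. Any diameter above 0 and below 1.0 cm is set to 1.0 cm. SPD is the sum of PPDs. The trigger is SPD ≥ 1.5 x nadir SPD. Normal size is LD ≤ 1.5 cm. There are one to six index nodes.

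**Reproducing the protocol's figure.** A 0.9 x 0.8 cm node is scored 1.0 x 1.0 = 1.0 cm², the default PPD stated in Section 7.4.1.

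**Case 1, reappearance.** At nadir, one node is 0.9 x 0.8 cm and one has vanished: SPD = 1.0 + 0 = 1.0. Later the vanished node is visible at 0.3 x 0.3 cm: SPD = 1.0 + 1.0 = 2.0, **+100%, PD**. True areas are 0.72 and 0.72 + 0.09 = 0.81 cm², +12%. Any reappearance below 1.0 cm, such as 0.5 cm, is scored the same.

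**Case 2, splitting.** A remnant of 1.4 x 1.2 cm has SPD 1.68. Three 0.4 cm fragments are scored 3 x 1.0 = 3.00, and 3.00/1.68 gives **+79%, PD**. True area is 3 x 0.16 = 0.48 cm², a fall of 71%.

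**Case 3, missing floor only.** Six nodes at the default have SPD 6.0. All grow to 1.25 x 1.25 cm: 6 x 1.5625 = 9.375, **+56%, PD**, with every node normal-sized. This is real regrowth, and the default softens it. In the close variant from 0.9 x 0.8 to 1.3 x 1.2 cm, scored SPD goes from 6.00 to 9.36 (+56%), while true area goes from 4.32 to 9.36 (+117%). The case shows the missing floor, not a default artefact.

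No node or fragment in these cases exceeds 1.5 cm, so the individual-node trigger does not fire.

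**Where the conflict can occur.** With n index nodes all at LD ≤ 1.5 cm, SPD is at most 2.25n. A 50% rise then needs nadir SPD ≤ 2.25n/1.5 = 1.5n cm²: 1.5 for one node, 9.0 for six. Index nodes must have a diameter above 1.5 cm at baseline, so all of them must have shrunk to normal size.

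**Dependence on the number of nodes.** One reappearance adds 1.0 cm², so it triggers alone only if nadir SPD ≤ 2.0. With five visible default nodes it is 5 to 6, +20%, no PD. With four visible and two reappearing it is 4 to 6, +50%, PD (true areas 2.88 to 3.06, +6%).

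**Measurement error, illustration only.** The protocol gives no error SD. Assuming 0.10 to 0.30 cm per diameter, seven scans and no true change, a subject whose index disease is stable 1.2 x 1.0 cm nodes meets the SPD trigger with all nodes still normal-sized in 3% to 34% of simulations with one node, 0% to 7% with two, and about 0% with six.

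**The case against.** **The IRC must confirm.** Section 5.8 requires IRC confirmation before study drug stops, and the closing note of Section 7.5.4 keeps uncertain cases on treatment under close observation. This mitigates the problem. It does not cure it: under Section 7.5 the IRC categorises by these same definitions, its findings are primary for PFS (Sections 7.1 and 10.4.2), and the note sets no SPD floor. The charter is not available, so it may contain a convention that helps.

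**Normal size and PD are not contradictory in themselves.** PD is measured from nadir, and CR has many other criteria. That is fair for Case 3. It does not rescue Cases 1 and 2, where the event is created by an assigned value.

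**The cases need few index nodes.** Largely true. However, inclusion criterion 4 (Section 4.2.1) admits subjects with a single measurable node, and two simultaneous reappearances among six nodes suffice. The split-node rule is written for a large mass; nothing in it excludes a mass that has since shrunk.

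**Stronger readings to avoid.** A reader might infer that these events fall mainly in Arm A, citing the 81.5% nodal response with single-agent idelalisib and the 17/21 marked reductions with ofatumumab (Section 1.3.5.2). Those figures describe reductions of at least 50% or marked shrinkage, not normalisation of every node; the reported CR rate with the combination was 2/21, though CR also needs non-nodal criteria. A reader might also infer that any remnant after a zero nadir is PD. A percentage rise from zero is undefined, and the protocol does not address it.

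**Conclusion.** The point holds in a limited zone and should be fixed. As written, the SPD trigger can score a primary-endpoint event while every index node is normal by the protocol's own standard, and in one case while true nodal area falls by 71%. The root cause is the missing floor. The 1.0 cm default and the count-every-fragment rule create the event in the reappearance and splitting cases, but soften it in concordant regrowth.

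The zone is bounded: nadir SPD of at most 1.5 cm² per index node, hence deep nodal responders, and mainly those with few index nodes. How many subjects enter it cannot be derived from the protocol. The worked cases depend only on the stated rules read literally; the measurement-error percentages depend on an assumed SD and are not trial frequencies.

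More such events in Arm A, pulling the hazard ratio toward 1, is plausible but an inference. If it occurred, the cost would be power and an understated effect, not a false claim of superiority.

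**What to change.** Reconcile Sections 7.4.1, 7.5.1 and 7.5.4 for endpoint scoring, and carry the result into the IRC charter. Two sentences would do it:

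1. SPD progression also requires that at least one index node or sub-component which has itself increased from its own nadir now measures more than 1.5 cm in LD and more than 1.0 cm in LPD.
2. Default values assigned to sub-centimetre fragments of a split node, or to sub-centimetre index nodes that reappear, do not count toward the 50% increase.

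The floor is the one already used in the next bullet of Section 7.5.4; the sponsor should confirm it.

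Both sentences are needed, because a bare floor can be met by an unchanged residual node. A stable 1.7 x 1.1 cm node (1.87 cm²) plus one node visible again at 0.3 cm gives 2.87, +53%, still PD. A 3.0 cm² mass splitting into one 1.6 x 1.1 cm piece (1.76) and three sub-centimetre fragments gives 4.76, +59%, still PD. With both sentences, neither scores PD, and nor do Cases 1 to 3.

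The cost is the text change and the charter update, with no new scans or readers. The downside is that a few SPD progressions made up only of nodes of 1.5 cm or less would be called at a later scan. How the study-drug discontinuation provisions, which rely on the same definition, should be aligned is for the sponsor to settle.
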